#### 8.3.1.1 Classification of an Adverse Event

The determination of seriousness, severity, and causality will be made by an on-site investigator who is qualified (licensed) to diagnose AE information, provide a medical evaluation of AEs, and classify AEs based upon medical judgment. This includes but is not limited to physicians, physician assistants, and nurse practitioners.

#### 8.3.2 Definition of Serious Adverse Events

An adverse event or suspected adverse reaction is considered "serious" if, in the view of either the investigator or sponsor, it results in any of the following outcomes (21 CFR 312.32 (a)):

- death
- a life-threatening adverse event
- inpatient hospitalization or prolongation of existing hospitalization
- a persistent or significant incapacity or substantial disruption of the ability to conduct normal life functions, or
- a congenital anomaly/birth defect.

Important medical events that may not result in death, be life-threatening, or require hospitalization may be considered serious when, based upon appropriate medical judgment, they may jeopardize the patient or subject and may require medical or surgical intervention to prevent one of the outcomes listed in this definition. Examples of such medical events include allergic bronchospasm requiring intensive treatment in an emergency room or at home, convulsions that do not result in inpatient hospitalization, etc.

SAEs will be:

- Assessed for severity and relationship to study product and alternate etiology (if not related to study product) by a licensed study clinician listed on the Form FDA 1572 or by the Institution as the site Principal Investigator or Sub-Investigator.
- Recorded on the appropriate SAE data collection form and eCRF.

- Followed through resolution by a licensed study clinician (for investigational new drug application [IND] studies, a licensed clinician listed on the Form FDA 1572 as the site Principal Investigator or Sub-Investigator).
- Reviewed and evaluated by DMID, an Independent Safety Monitor (ISM) (as deemed necessary), the Safety Monitoring Committee (SMC) (periodic review unless related), and the IRB/IEC.

#### 8.3.2.1 Suspected Unexpected Serious Adverse Reactions (SUSAR)

A SUSAR is any SAE where a causal relationship with the study product is at least a reasonably possible but is not listed in the Investigator Brochure, Package Insert or Summary of Product Characteristics.

#### 8.3.2.2 Severity of Event

All AEs or SAEs will be assessed for severity, according to the toxicity grading scales in Appendices A and B.

For adverse events (AEs) not included in the protocol defined grading system, the following guidelines will be used to describe severity.

- Mild (Grade 1): Events that are usually transient and may require only minimal or no treatment or therapeutic intervention and generally do not interfere with the subject's usual activities of daily living.
- Moderate (Grade 2): Events that are usually alleviated with additional specific therapeutic intervention. The event interferes with usual activities of daily living, causing discomfort but poses no significant or permanent risk of harm to the research participant.
- Severe (Grade 3): Events interrupt usual activities of daily living, or significantly affect clinical status, or may require intensive therapeutic intervention. Severe events are usually incapacitating.

AEs characterized as intermittent require documentation of onset and duration of each episode. The start and stop date of each reported AE will be recorded on the appropriate data collection form and eCRF. Changes in the severity of an AE will be documented to allow an assessment of the duration of the event at each level of intensity.

#### 8.3.2.3 Relationship to Study Intervention

The licensed study clinician's assessment of an AE's relationship to study product is part of the documentation process, but it is not a factor in determining what is or is not reported in this study. If there is any doubt as to whether a clinical observation is an AE, the event should be reported. The relationship to study product must be assessed for AEs using the terms: related or not related. In a challenge, the study product must always be suspect. To help assess, the following guidelines are used:

• Related – The AE is known to occur with the study intervention, there is a reasonable possibility that the study intervention caused the AE, or there is a temporal relationship between the study intervention and event. Reasonable possibility means that there is evidence to suggest a causal relationship between the study intervention and the AE.

• Not Related – There is not a reasonable possibility that the administration of the study intervention caused the event, there is no temporal relationship between the study intervention and event onset, or an alternate etiology has been established.

#### 8.3.3 Time Period and Frequency for Event Assessment and Follow-Up

In this study, solicited symptoms of influenza infection will be collected from the time of challenge through 7 days post-challenge and will **not** be considered adverse events.

Any influenza signs, symptoms or lab findings determined by the clinician to have exceeded the expected severity of a mild or moderate influenza symptom or sign will be considered unsolicited adverse events and captured on the appropriate data collection form and electronic case report form (eCRF). Events that are not consistent with illness due to influenza will be considered unsolicited AEs as well. Unsolicited AEs will be captured starting at the time of challenge through 28 days post-challenge. Information to be collected for AEs includes event description, date of onset, assessment of severity, relationship to study product and alternate etiology (assessed only by those with the training and authority to make a diagnosis and listed on the Form FDA 1572 as an investigator), date of resolution, seriousness and outcome. AEs occurring during the study will be documented appropriately regardless of relationship. AEs will be followed through resolution. Resolution of an AE is defined as the return to pretreatment status or stabilization of the condition with the expectation that it will remain chronic.

Any chronic or stable medical condition (Section 5.1) that is present at the time that the subject is screened will be considered as baseline and not reported as an AE. However, if the severity of any pre-existing medical condition increases, it should be recorded as an AE.

#### 8.3.4 Adverse Event Reporting

#### 8.3.4.1 Investigators Reporting of AEs

Information on all AEs should be recorded on the eCRF. All clearly related signs, symptoms, and results of diagnostic procedures performed because of an AE should be grouped together and recorded as a single diagnosis. If the AE is a laboratory abnormality that is part of a clinical condition or syndrome, it should be recorded as the syndrome or diagnosis rather than the individual laboratory abnormality. Each AE will also be described in terms of duration (start and stop date), severity, association with the study product, action(s) taken, and outcome.

#### 8.3.5 Serious Adverse Event Reporting

#### 8.3.5.1 Investigators Reporting of SAEs

Any AE that meets a protocol-defined serious criterion must be submitted immediately (within 24 hours of site awareness) on an SAE form to the DMID Pharmacovigilance Group, at the following address:

DMID Pharmacovigilance Group

Clinical Research Operations and Management Support (CROMS)

[name] [name] 650

[name]

SAE Hot Line: [name] (US) or [name] (outside US) SAE [contact] (US) or [name] (outside US) SAE Email Address: [contact]

In addition to the SAE form, select SAE data fields must also be entered into the DCC system. Please see the protocol-specific MOP for details regarding this procedure.

Other supporting documentation of the event may be requested by the DMID Pharmacovigilance Group and should be provided as soon as possible. The site will send a copy of the SAE report(s) to the ISM (as deemed necessary) when they are provided to the DMID Pharmacovigilance Group. The DMID Medical Monitor will review and assess the SAE for regulatory reporting and potential impact on study subject safety and protocol conduct.

At any time after completion of the study, if the site principal investigator or appropriate subinvestigator becomes aware of an SAE that is suspected to be related to study product, the site principal investigator or appropriate sub-investigator will report the event to the DMID Pharmacovigilance Group.

#### 8.3.5.2 Regulatory Reporting of SAEs

Following notification from the site Principal Investigator or appropriate sub-investigator, DMID, as the IND sponsor, will report any suspected unexpected serious adverse event (SUSAR) as an IND safety report to the FDA and will notify all participating site Principal Investigators (i.e., all Principal Investigators to whom the sponsor is providing drug under its IND(s) or under any Principal Investigator's IND(s) of potential serious risks from clinical studies or any other source, as soon as possible. DMID will report to the FDA any unexpected fatal or life-threatening suspected adverse reaction as soon as possible, but in no case later than 7 calendar days after the sponsor's initial receipt of the information. If the event is not fatal or life-threatening the IND safety report will be submitted within 15 calendar days after the sponsor determines that the information to an IND safety report will be submitted as soon as the information is available. Upon request from FDA, DMID will submit to the FDA any additional data or information that the agency deems necessary, as soon as possible, but in no case later than 15 calendar days after receiving the request.

SAEs that are not SUSARs will be reported to the FDA at least annually in a summary format which includes all SAEs.

#### 8.3.6 Reporting of Pregnancy

Pregnancies occurring in study subjects will be reported via Advantage electronic data capture system (Advantage eClinical) on the Pregnancy Report form. With the subject's permission, a venous blood sample for serological assays will be collected per protocol; however large volume blood samples for cellular immunological assays will be discontinued, and the subject will continue to be followed for safety for the duration of this study.

## 8.4 Unanticipated Problems

#### 8.4.1 Definition of Unanticipated Problems (UP)

The Department of Health and Human Services Office for Human Research Protections (OHRP) considers unanticipated problems involving risks to participants or others to include, in general, any incident, experience, or outcome that meets all of the following criteria:

- Unexpected in terms of nature, severity, or frequency given (a) the research procedures that are described in the protocol-related documents, such as the Institutional Review Board (IRB)-approved research protocol and informed consent document; and (b) the characteristics of the participant population being studied;
- Related or possibly related to participation in the research ("possibly related" means there is a reasonable possibility that the incident, experience, or outcome may have been caused by the procedures involved in the research); and
- Suggests that the research places participants or others at a greater risk of harm (including physical, psychological, economic, or social harm) than was previously known or recognized.

#### 8.4.2 Unanticipated Problem Reporting

The investigator will report unanticipated problems (UPs) to the reviewing Institutional Review Board (IRB) and to the Statistical and Data Management Coordinating Center (SDMCC)/study Sponsor and the lead principal investigator (PI). The UP report will include the following information:

- Protocol identifying information: protocol title and number, PI's name, and the IRB project number;
- A detailed description of the event, incident, experience, or outcome;
- An explanation of the basis for determining that the event, incident, experience, or outcome represents an UP;
- A description of any changes to the protocol or other corrective actions that have been taken or are proposed in response to the UP.

To satisfy the requirement for prompt reporting, UPs will be reported using the following timeline:

- UPs that are serious adverse events (SAEs) will be reported to the IRB and as per Section 8.3.5 Serious Adverse Event Reporting within 24 hours of the investigator becoming aware of the event.
- Any other UP will be reported to the IRB and to the DCC/study sponsor within three days of the investigator becoming aware of the problem.

## 9. STATISTICAL CONSIDERATIONS

#### 9.1 Introduction

The goal of this study is to find a challenge virus dose that is safe and can achieve a symptomatic influenza AR that will be sufficiently high for utilization in future vaccine or intervention studies. The optimal dose of the three considered is broadly defined as the minimum challenge virus dose that elicits the highest AR without meeting safety-stopping criteria. Additionally, viral recovery, clinical symptoms, and immune responses over the post-challenge period will be described by challenge dose group.

## 9.2 Statistical Hypotheses

The study is not designed to achieve predetermined levels of power or precision to address the primary, secondary, or exploratory objectives. It is of interest to utilize more of the available sample size at higher doses, unless there is adequate evidence that one of the lower doses is sufficiently infectious. This is further described in Section 9.3.2. General methodology planned to address study objectives is described in Section 9.5, and the specific null and alternative hypotheses and details about planned tables, figures, and listings will be given in a separate statistical analysis plan (SAP).

## 9.3 Sample Size Determination

#### 9.3.1 Study Design

This is a challenge study of A/Texas/71/2017 (H3N2), clade 3C3a virus infection to assess viral dynamics, clinical and immunological response, and safety. A targeted maximum of114 (targeting 106 active plus 8 shams) participants will be enrolled at the clinical sites and will receive one of 3 doses (10^4, 10^5, or 10^6 TCID50) of A/Texas/71/2017 (H3N2), clade 3C3a virus or sham placebo. There will be a targeted maximum of 36 active subjects enrolled into each challenge dose group. For each challenge cohort, a target of 1 sham placebo subject will also be included, with the primary intent of reducing the rate of false positive symptoms due to subjects not being certain whether they are receiving active virus.

Initially, a targeted total of 12 subjects will be enrolled to receive a dose of  $10^4$  TCID50, as well as 1 sham placebo subject. While it is unexpected that this dose would be highly infective, this initial cohort will allow for a safety assessment of the virus and study challenge procedures. The criteria for determining the dose received by the subsequent cohort will then depend on the percentage of those initial subjects meeting the symptomatic influenza criteria, and whether the study stopping-safety criteria have been met. The doses received by each subsequent challenge cohort will be determined in a similar manner, as depicted in **Figure 1**. At the highest dose, both challenge cohorts would include a target of 17 active subjects and 1 sham, in order to increase the total sample size at what are assumed to be doses more likely to meet the criteria for optimality. Escalation will stop when the maximum sample size is reached.

[figure not shown]
#### 9.3.2 Dose Escalation and Sample Size Allocation

The study is planned to target enrolling a maximum of 114 subjects (targeting 106 active plus 8 shams), at one of 3 challenge virus doses or sham placebo. While the study is not designed to test any specific null hypothesis or reach a pre-determined level of estimation precision, this section gives the precision for estimates and power for hypothesis tests of interest, based on this proposed sample size. Adjustments to p-values in the presence of multiple comparisons may be made, depending on the objective, but the calculations below do not account for this possibility. Details on adjustment for multiple comparisons are given in Section 9.5.1 and will be described further in the SAP.

A targeted total of 13 participants (12 active plus 1 sham) will be planned to enroll for each cohort at the two lowest dose levels, and a targeted total of 18 participants (17 active plus 1 sham) per cohort for the highest dose level. Additional randomization slots will be included to allow for the possibility of enrolling beyond the targeted cohort sizes. These calculations allow for 2 subjects per cohort (of the targeted sizes) to withdraw prior to challenge, and if that does not happen, or if more than the targeted number of subjects are enrolled in a given cohort or dose group, the power and precision would increase (detectable difference would decrease) compared to what is presented in this section. Correspondingly, if more than 2 subjects withdraw the power and precision would decrease.

The dose escalation decision rules have been constructed with the intent of safely escalating doses until there is compelling evidence of a sufficiently high AR at a given dose. Since it is assumed that the AR will increase with the dose, the symptomatic influenza thresholds for dose escalation from one cohort to the next were chosen to increase the expected sample size at the higher doses and improve the precision for estimating the true AR for those doses.

[figure not shown]
**Figure 2** shows the probability of meeting the infection threshold for further enrollment at a dose, given varying numbers of subjects enrolled at that dose (10 enrolled in Cohorts 1A or 2A, 15 at Cohort 3A, or 20 in Cohorts 1A+1B or 2A+2B), varying true infection probabilities, and the thresholds for further enrollment.

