### Safety Threshold

The safety threshold is defined as meeting one of the protocol-defined halting criteria outlined in Section 7.1.1 which includes the occurrence of severe influenza complications in any study subject (Section 2.3.1). If a subject has a severe influenza complication(s), the study staff and subject will be unblinded as to receipt of challenge virus or sham and as to the results of influenza RT-PCR testing for safety evaluation and potential therapeutic intervention with an approved influenza antiviral agent.

In this adaptive schema, the initial cohort (Cohort 1A) for the lowest challenge dose group will include a targeted total of 12 subjects receiving 10^4 TCID50 of the challenge strain and one subject receiving sham placebo. If fewer than 80% of subjects meet the case definition for influenza in Cohort 1A, the dose will escalate to 10^5 TCID50 to include Cohort 2A. If 80% or more subjects in Cohort 1A meet the case definition for influenza, the lowest challenge dose group will be expanded to include a targeted total of 12 additional subjects receiving 10^4 TCID50 of the challenge strain and one subject receiving sham placebo to comprise Cohort 1B. Cumulatively, if fewer than 80% of subjects in Cohorts 1A and 1B meet the case definition for influenza, the dose will escalate to 10^5 TCID50 to include Cohort 2A. If 80% or more of the subjects in Cohorts 1A and 1B meet the case definition for influenza than the lowest challenge dose group will be expanded to include a targeted total of 12 additional subjects receiving 10^4 TCID50 of the challenge strain and one subject receiving sham placebo to comprise Cohort 1C. Cumulatively, if fewer than 80% of subjects in Cohorts 1A, 1B, and 1C meet the case definition for influenza the dose will escalate to 10^5 TCID50 to include Cohort 2A. If 80% or more of the subjects in Cohorts 1A, 1B, and 1C combined meet the case definition for influenza then the optimal dose of 10^4 TCID50 will be selected.

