# Figure 2. Probabilities of further enrollment at the current dose, given varying true infection probabilities, numbers of subjects enrolled at the current dose, and decision thresholds

For illustration, with n=10 subjects enrolled in Cohort 1A at  $10^4$  TCID50, the probability of achieving 8 infections (solid line, top left panel) would be only 0.01 if the true infection probability were 0.4, compared to 0.67 if the true infection probability were 0.8.

Depending on the number of infections observed at each dose level, the final sample size for each dose group will be approximately 10, 15, 20 or 30. Figure 3 shows the estimated infection probabilities and associated exact 95% confidence intervals that would result from observing varying numbers of symptomatic influenza events at a given dose level. The maximum CI width occurs at 50% observed events. With 30 subjects enrolled at the optimal dose, this would correspond to observing 15 symptomatic influenza events and an estimated CI of (31.3%, 68.7%).

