4.4.1. Sample Size Considerations

Figure 2 shows the probability of meeting the infection threshold for further enrollment at a dose, given varying numbers of participants enrolled at that dose (10 enrolled in Cohorts 1A or 2A, 15 at Cohort 3A, or 20 in Cohorts 1A+1B or 2A+2B), varying true infection probabilities, and the thresholds for further enrollment. For illustration, with n=10 participants enrolled in Cohort 1A at 10^4 TCID₅₀, the probability of achieving 8 infections would be only 0.01 if the true infection probability were 0.4, compared to 0.38 if the true infection probability were 0.7.

Depending on the number of infections observed at each dose level, the final sample size for each dose group would be approximately 10, 15, 20 or 30. Figure 3 shows the estimated infection probabilities and associated exact 95% confidence intervals that would result from observing varying numbers of symptomatic influenza events at a given dose level. The maximum CI width occurs at 50% observed events. With 30 participants enrolled at the optimal dose, this would correspond to observing 15 symptomatic influenza events and an estimated CI of (31.3%, 68.7%).

Table 2 gives the probability of observing one or more safety events, such as a solicited symptom or an AE of a particular classification in varying total dose group sizes, given underlying true event probabilities.

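### Protocol 9.3.2 says power would rise if the assumed withdrawals do not occur, but the Figure 2 probability of staying at a dose is lower at the planned 12 virus recipients than at the 10 shown

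*Protocol*

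**What the plan says.** Protocol 9.3.2 sets the cohort size at the two lower doses: "A targeted total of 13 participants (12 active plus 1 sham) will be planned to enroll for each cohort". It states the allowance behind its figures: "These calculations allow for 2 subjects per cohort (of the targeted sizes) to withdraw prior to challenge". Figure 2 is accordingly drawn for "10 enrolled in Cohorts 1A or 2A, 15 at Cohort 3A, or 20 in Cohorts 1A+1B or 2A+2B". The section then says that without those withdrawals, and equally "if more than the targeted number of subjects are enrolled in a given cohort or dose group, the power and precision would increase", compared with what it presents. With more than two withdrawals, it says, they would decrease.

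The rule itself is a percentage. Under the Safety Threshold heading in Protocol 4.1, the dose goes up to 10^5 "If fewer than 80% of subjects meet the case definition for influenza in Cohort 1A", and the same dose is expanded "If 80% or more subjects in Cohort 1A meet the case definition for influenza". At 10^5 the corresponding cut-off is 70%, applied cumulatively.

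The worked example under Figure 2 takes n=10 in Cohort 1A and gives a probability of 0.01 of reaching the threshold when the true infection probability is 0.4, "compared to 0.67 if the true infection probability were 0.8". SAP 4.4.1 repeats the example at n=10 with a different second value, "compared to 0.38 if the true infection probability were 0.7". Neither document gives a value at n=12.

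**The concern.** Section 9.3.2 announces precision for estimates and power for hypothesis tests, but prints no test power and no detectable difference. It contains Figure 2 (probability of meeting the threshold for further enrolment), Figure 3 (confidence intervals) and Table 3 (probability of seeing at least one safety event). Figure 2 is the only one that describes how the escalation rule behaves, and it is computed at the sizes left after the withdrawals.

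A reader who takes the sentence at face value will expect a fully enrolled Cohort 1A to do better than the printed 0.67. A percentage applied to a whole number of cases does not work that way: 8 of 10 is exactly 80%, but no count out of 12 is, and 9 of 12 is 75% and escalates. What is at stake is an accurate account of how often the design stays at a dose whose true attack rate is at or near the cut-off, at the size actually planned.

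**Working it through.** **Inputs.** Target of 12 virus recipients per cohort at the two lower doses, and 10 after two withdrawals (Protocol 9.3.2, taking both withdrawals as virus recipients, as its n=10 implies). Cut-offs of 80% at 10^4 and 70% at 10^5 (Protocol 4.1 and 4.3). Printed values 0.01 and 0.67 (Protocol 9.3.2) and 0.38 (SAP 4.4.1). Cohort 3A is left out because the text states no cut-off for it.

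**Formula.** With n virus recipients, true attack rate p and cut-off t, the probability of staying is P(X ≥ r), where X is binomial(n, p) and r is t × n rounded up to a whole number.

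**Reproducing the printed figures.** At n=10 and t=0.8, r=8. For p=0.8:

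45 × 0.8^8 × 0.2^2 + 10 × 0.8^9 × 0.2 + 0.8^10 = 0.302 + 0.268 + 0.107 = 0.678.

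The printed 0.67 looks truncated rather than rounded. The same formula gives 0.012 at p=0.4 (printed 0.01) and 0.383 at p=0.7 (printed 0.38). Exactly 8 cases would give 0.302, so the printed figure is the upper tail.

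**At the planned size.** At n=12, 0.8 × 12 = 9.6, so r=10, an effective bar of 83.3%. For p=0.8:

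66 × 0.8^10 × 0.2^2 + 12 × 0.8^11 × 0.2 + 0.8^12 = 0.283 + 0.206 + 0.069 = 0.558.

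The cumulative rows below treat the look as a single test on the pooled count.

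| Look | True rate | After two withdrawals per cohort | At target |
|---|---|---|---|
| 1A, 80% | 0.4 | 8/10: 0.012 | 10/12: 0.003 |
| 1A, 80% | 0.6 | 0.167 | 0.083 |
| 1A, 80% | 0.7 | 0.383 | 0.253 |
| 1A, 80% | 0.8 | 0.678 | 0.558 |
| 1A, 80% | 0.9 | 0.930 | 0.889 |
| 1A, 80% | 0.95 | 0.988 | 0.980 |
| 1A+1B, 80% | 0.8 | 16/20: 0.630 | 20/24: 0.460 |
| 2A, 70% | 0.7 | 7/10: 0.650 | 9/12: 0.493 |
| 2A, 70% | 0.8 | 0.879 | 0.795 |
| 2A+2B, 70% | 0.8 | 14/20: 0.913 | 17/24: 0.911 |
| 2A+2B, 70% | 0.85 | 0.978 | 0.980 |

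Passing all three looks at 10^4 with a true rate of 0.8 has probability 0.468 with 10 per cohort and 0.346 with 12.

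**Other sizes.** Under the 80% rule at a true rate of 0.8, n=11 (9 needed) gives 0.617, n=13 (11) 0.502, n=14 (12) 0.448 and n=15 (12) 0.648. The probability falls until the cut-off is again an exact whole number, then jumps up.

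**Quantities that do improve.** At 50% observed, the exact 95% interval narrows from 31.3–68.7% (15/30, as printed) to 32.9–67.1% (18/36). The chance of seeing at least one event of true probability 10% rises from 65.1% (n=10, as in Table 3) to 71.8% (n=12).

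**Denominator.** SAP 4.1 says the attack rate was determined across everyone in the cohort, blinded to sham. If the one sham is counted and is not a case, 10+1 needs 9 of 11 and 12+1 needs 11 of 13. At a true rate of 0.8 among virus recipients these give 0.376 and 0.275. Both are lower, and the direction is the same.

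**The case against.** The strongest reply is that the sentence is generic wording about test power. It glosses power as a smaller detectable difference, which a continuation probability does not have, and the documents never call Figure 2 power. That is a fair reading of where the wording came from. It does not settle the matter, because the sentence covers what the section presents, makes no exception for Figure 2, and there is no test power in the section for it to describe.

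Several other points stand:

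- Apart from 0.67 being truncated, no printed number is wrong. Each worked example is explicitly conditional on n=10.
- SAP 4.4.1 does not carry the disputed sentence. Its only gap is that it gives nothing at the planned size.
- The study disclaims predetermined power or precision (Protocol 9.2, SAP 4.4). That excuses having no target, but not a wrong direction for a reported operating characteristic.
- Protocol 9.3.2 says the thresholds were chosen to put more of the sample at higher doses. A stricter bar at n=12 fits that intent, and it roughly halves or better the chance of staying at a dose with a true rate of 0.6 or 0.4.
- A cohort of 12 is the target, not a certainty. Backups are confined (4.1) and extra randomization slots exist, but drop-outs within 48 hours of challenge are not replaced (6.3.2).

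**Conclusion.** The statement is wrong as it applies to Figure 2 and right for Figure 3 and Table 3. Counting virus recipients only, going from the assumed to the planned size lowers the Cohort 1A probability by 12 points at a true rate of 0.8 (0.68 to 0.56) and 13 points at 0.7 (0.38 to 0.25). Cumulative 1A+1B falls by 17 points at 0.8 (0.63 to 0.46), and Cohort 2A by 16 points at 0.7 (0.65 to 0.49). For Cohort 1A the loss shrinks to 4 points at 0.9 and 1 point at 0.95.

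Four stronger readings are tempting and not supported:

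- A reader might infer that the protocol offers 0.67 as a guaranteed minimum. It does not, since it also says the figures fall with more than two withdrawals.
- A reader might infer that continuation probabilities always fall as n grows. They saw-tooth: 0.448 at n=14 but 0.648 at n=15, and 2A+2B is nearly flat at a true rate of 0.8.
- A reader might infer that these probabilities are the reason given for the 80% and 70% thresholds, or that the rule is worse at n=12. The stated reason is sample allocation to higher doses, and wrongful continuation also falls (0.012 to 0.003 at a true rate of 0.4).
- A reader might take 1 − 0.56 = 0.44 as the trial's actual rate of escalating past a true 80% dose after Cohort 1A. That holds only for a virus-recipient denominator. With the sham counted as in SAP 4.1, and not a case, the staying probability is 0.38 at 10+1 and 0.27 at 12+1.

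Staying here means further enrolment after a look, not final selection of the dose.

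**What to change.** In Protocol 9.3.2 and SAP 4.4.1:

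- Add n=12 and n=24 to Figure 2 beside n=10 and n=20, with the case counts the rule implies: 8/10, 10/12, 16/20 and 20/24 for 80%; 7/10, 9/12, 14/20 and 17/24 for 70%.
- Give the worked example at both sizes: 0.68 and 0.56 for a true rate of 0.8, and 0.38 and 0.25 for 0.7.
- State the denominator behind these values. If the sham is counted as in SAP 4.1, and assumed not to be a case, report 0.38 (9/11) and 0.27 (11/13) for a true rate of 0.8.

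In Protocol 9.3.2 only, limit the statement about increase to confidence-interval precision and the Table 3 probabilities. Add that continuation probabilities need not rise with n, and that for Cohorts 1A and 2A they are lower at n=12 than at n=10.

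The cost is a few sentences and one recomputed figure. The escalation rule, enrolment and procedures are untouched. The only downside is a less favourable stated probability at full enrolment.
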